6.7 Prior and Concomitant Medications

All prescription, nonprescription medications (e.g., over-the-counter [OTC]) drugs and herbal supplements) and non-medical treatments starting from 30 calendar days before Screening until end of the study must be recorded in source documents and the eCRF. For each medication, documentation should list the trade or generic name, the total daily dose including units (or the dose, units, and scheduled and actual frequency of administration if the medication is not taken daily), the route of administration, and the reason for use.

Changes, additions, or discontinuations to medications will be assessed and recorded in the eCRF during each study visit. All as-needed prescriptions should be converted to reflect actual dose taken per day.

Starting on the first day of the screening phase, after written informed consent for the study has been provided, all antipsychotic or other psychotropic medications will be stopped with clinically appropriate titration down as per the Investigator's clinical judgment. Patients will be

Confidential Page 49 of 102

instructed not to take any medication(s) during the conduct of the study unless approved by the Investigator. Any patient unable to be safely discontinued from current antipsychotic therapy or other psychotropic medications will not be eligible for the study. Any treatment other than the study treatment given will be considered a concomitant medication and will be documented in the eCRF. Any patient requiring emergency treatment with prescription or nonprescription medication during the screening phase through the EoS Visit will be approved by the Investigator. If the Investigator determines that the patient requires medication during the study, the Medical Monitor must be contacted within 24 hours.

Psychotropic medications are prohibited except for lorazepam as needed for agitation, restlessness, irritability, or hostility; zolpidem, zaleplon, or eszopiclone for insomnia; diphenhydramine or benztropine for EPS; and propranolol for akathisia.

Within the daily limits shown in 2, lorazepam, benztropine, and propranolol are not allowed on as needed basis; every administration must be considered and approved by the Investigator prior to administration.

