7.1 Schedule of Assessments

The study consists of a 7-day inpatients screening phase (up to a 7-day extension of the screening phase is allowed, if necessary with the approval of the Medical Monitor), Study Treatment Period (Days 1 to Day 28 including Baseline [Day 1]), Stabilization Period (up to 5 days, Days 29 to 33), and EoS Visit (Visit 7 [Day 42] ± 2 days). Therefore, the maximal study duration for an individual patient will be approximately up to 8 weeks.

Note, this is an inpatient study from Screening to the end of the Stabilization Period. The procedures to be performed throughout the study are outlined in the SoA (Table).

Confidential Page 53 of 102

Table do: Schedule of Assessments

Event	Screening Phase	Baseline	Study Treatment Period								End of Stabilization Period	End of Study Visit
Event	Up to 7 days ^a	Day 1	Days 2-7	Day 8 ±1	8 9-14	Day 15 ±1	Days 16-20	Day 21 ± 1	Days 22-27	Day 28 or ET	33°	Day 42± 2
Visit Number	1	2	NA ^b	3	NA ^b	4	NA ^b	5	NA ^b	6	7	8
Entrance/Screening Criteria												
Informed Consenta	X											
Admission to Inpatient Unit ^a	X											
Inclusion/Exclusion Criteria Review ^a	X	X										
Screening Adjudication Form(s) and Recordings ^d	X											
Medical History ^e	X											
MINI-Plus BPD 7.0.2	X											
Prior Medication Washout ^f	X											
Hepatitis/HIV	X											
Urine Drug and Blood Alcohol Screen ^g	X ^g											
Randomization		X										
Efficacy												
(PCRS) SCI-PANSS and CGI-S	X ^h	X ^h		X		X		X		Xh		
Cogstate Test	X^{i}	Xi								Xi		
Safety												
Prior and Concomitant Medication	X	X	X	X	X	X	X	X	X	X	X	X
Physical Exam ^j	X	X		X		X		X		X		X
AIMS	X	X^k		X^k		X^k		X^k		X^k		
SAS	X	X^k		X^k		X^k		X^k	_	X^k		
BARS	X	X^k		X^k		X^k		X^k		X^k		
C-SSRS	X ^l	X ^m		X ^m		X ^m		X ^m		X ^m	X ^m	X ^m
BMI and Waist Circumference ⁿ	X	X		X		X		X		X		

Page 54 of 102

	Screening Phase	Baseline Day 1	Study Treatment Period								End of Stabilization Period	End of Study Visit
Event	Up to 7 days ^a		Days 2-7	Day 8 ± 1	Days 9-14	Day 15 ± 1	Days 16-20	Day 21 ± 1	Days 22-27	Day 28 or ET	33°	Day 42± 2
Visit Number	1	2	NAb	3	NAb	4	NAb	5	NA ^b	6	7	8
Urine Pregnancy Test ^o	X	X								X	X	
Clinical Laboratories (for Screening and exclusionary purposes) ^p	X											
Hematology, Serum Chemistry including Prolactin, Urinalysis ^q	X	X		X		X		X		X		
TSH ^r	X									X		
PT, aPTT, and INR	X	X								X		
ACTH and Cortisol		X								X		
Resting 12-lead ECG ^s	X	X		X		X		X		X		

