- o. All positive urine pregnancy test results must be confirmed by a serum test. Patients with positive urine and serum pregnancy test results at Screening must not be enrolled. Patients with positive urine and serum pregnancy test results during the trial must discontinue treatment and be withdrawn from the trial. Pregnancy tests can be performed at any point during the trial if pregnancy is suspected.
- P. Clinical laboratory samples at Screening for exclusionary purposes are to be taken after a fast of at least 8 hours. Vital signs and ECG should be completed before any blood samples are collected. Clinical laboratory test results drawn within ± 24 hours of the scheduled timepoint may be used. Clinical laboratory tests will include the following (see Table 14.2: and Section 8.2.4):
 - Hematology Screening assessments (excluded test result) will include measurement of hemoglobin (≤9 g/dL or ≤90 g/L), platelets (≤75,000/µL or ≤75×10⁹/L), neutrophils (absolute ≤1000/µL or ≤1×10⁹/L).
 - Clinical chemistry tests for exclusionary purposes are for ALT (>2 × ULN), AST (>2 × ULN), creatinine (≥2 mg/dL or ≥176.8 μmol/L), CPK (≥3 × ULN, unless discussed with the Medical Monitor), HbA1c (≥7.0%), TSH. Important note: Free T4 will be measured only if the result for TSH is abnormal.
 - Creatinine clearance will be calculated at Screening using the Cockcroft-Gault equation; estimated creatinine clearance of <45 mL/min is exclusionary.
- Clinical laboratory samples are to be taken after a fast of at least 8 hours. Vital signs and ECG should be completed before any blood samples are collected. Clinical laboratory test results drawn within ± 24 hours of the scheduled timepoint may be used. Routine clinical laboratory tests to be monitored throughout the study will include the following:
 - Hematology will include measurement of hematocrit, RBC, reticulocytes, and WBC with differential.
 - Clinical chemistry will include measurement of albumin, ALT, ALP, amylase, AST, bicarbonate, bilirubin-total, blood urea nitrogen, calcium, creatine kinase, creatinine, gamma-glutamyl transpeptidase, globulin, glucose, lactate dehydrogenase, lipase, magnesium, phosphate, potassium, prolactin, sodium, total protein, total cholesterol, triglycerides, HDL, LDL and uric acid.
 - Urinalysis: pH of freshly voided specimen, specific gravity, protein, glucose, ketones, blood, and microscopic examination of the sediment.

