- Important note: Free T4 will be measured only if the result for TSH is abnormal.
- 5. Standard 12-lead ECGs (in triplicate) will be performed after the patient has been supine and at rest for ≥5 minutes. The captured ECGs must be separated by at least 1 minute. A central ECG service will be utilized to review all ECGs in order to standardize interpretations for the safety analysis. In addition, ECG results will be evaluated at the investigational site to monitor safety during the trial. Any Screening ECG with abnormal result(s) considered to be clinically significant should be repeated to confirm the finding(s) before excluding the patient from the trial. Patients will be randomized based on Screening ECG results from the central reader and Baseline ECG results from the trial site. If the Baseline ECG results from the central reader, when available, indicate a QTcF >450 msec at Baseline, the Investigator must contact the Medical Monitor to discuss the patient's continued participation in the trial. ECGs scheduled for the same visit as blood samples are to be completed before blood is drawn.
- Vital signs will include body temperature, SBP, DBP, and heart rate. Blood pressure and heart rate will be measured in the following order: supine, sitting and standing after the patient has been in each position for at least 3 minutes. Vital signs scheduled for the same visit as blood sample have to be completed before blood is drawn.

Confidential Page 56 of 102

- The recording of AEs is to start immediately after the ICF is signed and up to 14 days after the end of EoT.
- PK analyses will include the First 60 randomized patients regardless of cohort. PK blood samples will be collected on Day 1, 8, and 21 during the following timepoints after the morning dose: 15 minutes, 30 minutes, 1, 2, 3, 4, 8, and 24 hours. See protocol Section 8.3. On Day 1 only, a pre-dose PK blood sample will be collected. Samples are collected after ECGs and vital signs. The total volume of blood to be collected during the Screening, treatment, and End of Stabilization period is 161 mL. Approximately 21 mL of blood will be collected during the Screening Visit, 130 mL will be collected during the 28-day Treatment Period, and 10 mL will be collected during the End of Stabilization period.
- w. On Day 29 patients are to be started on standard antipsychotic medication as prescribed by the Investigator.

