7.2.10 Visit 6 (Study Day 28)

On Study Day 28, all assessments should be performed on the same day; the last day of study drug dosing is Day 28 and, if possible, when any patient discontinues prior to this visit, the following assessments will be performed:

• Recording of concomitant medications (e.g., prescription and nonprescription medications)

Confidential Page 62 of 102

- Full physical examination (if applicable)
- Bodyweight, BMI (derived programmatically from body weight and height measurements), and waist circumference
- Vital signs
- Resting 12-lead ECG (triplicate, further information in Section 8.2.3)
- Collection of blood and urine samples for clinical laboratory tests. Additional information is presented in the footnotes to the SoA (Table)
- Study drug administration
- Urine pregnancy test for all females of childbearing potential
- Assessment and recording of AEs
- PANSS. PCRS must be administered before PANSS
- CGI-S
- C-SSRS
- AIMS, 3 to 6 hours post-dose
- BARS, 3 to 6 hours post-dose
- SAS, 3 to 6 hours post-dose
- Cogstate test

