10 STATISTICS

10.1 General Procedures

The statistical analysis will be undertaken in collaboration with LB Pharmaceuticals Inc.

A detailed Statistical Analysis Plan (SAP) will be finalized and signed before database lock and before analysis of the study being carried out. Any deviations from the analyses described below will be included in the SAP, which will be included in the clinical study report.

Continuous variables will be summarized by treatment using descriptive statistics (n, mean, median, SD, minimum, and maximum). For categorical variables, frequencies and percentages will be presented by treatment. Baseline is defined as the last observation prior to initiation of study medication. Details of the statistical analyses will be provided in the SAP.

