### 5.2.2 Baseline

Baseline is defined as the last non-missing value (either scheduled, unscheduled, or repeat) before the patient receives the first dose of study drug.

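### The ±24-hour laboratory footnote reaches across the first dose on Day 1 and into Day 29, so some prolactin changes may start from a Screening value or end on a sample taken after standard antipsychotic treatment has begun

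*Protocol*

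**What the plan says.** **The window.** The schedule row "Hematology, Serum Chemistry including Prolactin, Urinalysis" is marked at Screening and on Days 1, 8, 15, 21 and 28 (or early termination). Its footnote says "Clinical laboratory samples are to be taken after a fast of at least 8 hours" and "Clinical laboratory test results drawn within ± 24 hours of the scheduled timepoint may be used". It mentions neither the first dose nor the antipsychotic restart.

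**The visits.** The schedule header gives Days 8, 15 and 21 a margin of one day either way and gives Days 1 and 28 none. For Day 28, Protocol Section 7.2.10 states: "On Study Day 28, all assessments should be performed on the same day".

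**Baseline.** Protocol Section 10.1: "Baseline is defined as the last observation prior to initiation of study medication". SAP Section 5.2.2: "Baseline is defined as the last non-missing value (either scheduled, unscheduled, or repeat) before the patient receives the first dose of study drug".

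**Prior and later antipsychotics.** Under Protocol Section 6.7, from the first day of screening after consent, "all antipsychotic or other psychotropic medications will be stopped with clinically appropriate titration down". At the other end, a schedule footnote says "On Day 29 patients are to be started on standard antipsychotic medication as prescribed by the Investigator", while Section 7.2.11 words the Day 29 start as optional.

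**Analysis.** SAP Section 5.13.2 plans descriptive laboratory summaries, change from baseline, and shifts against the normal range by arm and visit. The only visit windows in the SAP are in Table 3 (Section 5.2.4). They apply to early termination assessments, and Days 25 to 30 count as Day 28.

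**The concern.** Day 1 and Day 28 are the two visits where the hour of a blood draw matters most. Study drug begins on the first, and another antipsychotic can begin the day after the second. The footnote applies one symmetric margin to all visits, including these two.

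Prolactin is the analyte at stake. It is a named safety endpoint, and Protocol Section 1.4 calls its elevation the most notable Phase 1 safety result. The SAP has no between-arm model for laboratory data, so what the reader sees is each arm's change from baseline and its shift table. If the starting value is already raised by a previous drug, the reported rise shrinks and the patient cannot be counted as moving from normal to high. If the final value follows a dose of another antipsychotic, it may carry that drug's effect, in the placebo arm as well as the active arms.

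**Working it through.** The plan states no figure on this point to reproduce. The check is a comparison of timing rules with some short arithmetic.

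**Step 1: what the footnote reaches.** Add and subtract one day at each visit.

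| Visit | Margin in schedule header | Reach of ±24 h | Treatment event inside that reach |
|---|---|---|---|
| Day 1 | none | day before first dose to Day 2 | first dose of study drug |
| Day 8 | ±1 day | Days 7 to 9 | none |
| Day 15 | ±1 day | Days 14 to 16 | none |
| Day 21 | ±1 day | Days 20 to 22 | none |
| Day 28 | none | Days 27 to 29 | start of standard antipsychotic |

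The footnote opens a margin at exactly the two visits that the header holds fixed.

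**Step 2: what happens to a post-dose Day 1 prolactin.** Both Baseline definitions reject it. Unless an unscheduled or repeat pre-dose value exists, the only earlier scheduled prolactin is the Screening one, taken up to 7 days before the first dose, or 7 + 7 = 14 days if screening is extended. Under the schedule's washout footnote, washout starts only after consent and confirmation of the diagnosis. Exclusion criterion 22 requires at least 5 half-lives off a prohibited psychotropic before Baseline, so with first-order elimination at most 2^(−5) = 0.031, about 3%, remains on Day 1. (Depot drugs have their own rule, one and a half injection cycles.) No such limit applies at Screening.

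**Step 3: can one dose move prolactin?** Protocol Section 14.2.1 gives cases at or above 100 µg/L by dose. Single-dose cohorts (10, 50, 100, 150, 200 mg): 1 + 3 + 1 + 1 + 0 = 6. Twice-daily cohorts: 2 + 1 + 2 = 5. The sum, 6 + 5 = 11, matches the stated total. With 5 cohorts of 6 on active drug, 6/30 = 20% of single-dose volunteers were affected, taking one case per volunteer. A post-dose Day 1 prolactin is therefore rightly barred from being Baseline, and the draw has to be pre-dose to be of use as one.

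**Step 4: is Day 29 itself the problem?** The fraction of LB-102 left 24 hours after a dose is 2^(−24/t½). Using the shortest and longest mean half-lives in Protocol Table 14.1:

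- t½ = 11.933 h: 2^(−24/11.933) = 0.248
- t½ = 14.146 h: 2^(−24/14.146) = 0.309

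A fasting Day 29 morning sample taken before any other antipsychotic is about 24 hours after the Day 28 dose. A pre-dose Day 28 sample stands in the same position to the Day 27 dose. Such a value is comparable. The difficulty arises only when the new antipsychotic is given before the draw.

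**Step 5: does anything downstream catch it?** SAP Section 5.13.2 has no laboratory window and no rule about a sample drawn after the antipsychotic start. Table 3 can also carry an early termination value from Day 29 or 30 into Day 28 when the planned visit was missed or incomplete.

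**The case against.** The strongest reply is that the plan already points the right way. The Day 1 column is headed Baseline. Protocol Section 7.2.2 lists blood collection before randomization and dosing, and labels its post-dose items as such. Section 7.2.10 is specific to Day 28 and can be read as overriding a general and permissive footnote. Samples follow an overnight fast. Some patients will have stopped their previous antipsychotic before Screening. All of this lowers the likely number of affected samples. It does not close the gap: list order is not a rule, fasting governs food and not dosing, and where the protocol wants a timed sample it says so, as for the Day 1 pharmacokinetic draw.

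Four stronger readings are tempting and are not supported:

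- **That change is measured from a post-dose Day 1 value.** Both Baseline definitions prevent this; the consequence is the fallback to Screening.
- **That half of the 48-hour window is on the wrong side at Day 28.** The antipsychotic starts on Day 29, not at the Day 28 timepoint. With an assumed 08:00 timepoint, 8 of 48 hours (17%) fall on Day 29; with noon, 12 of 48 (25%). Those hours matter only if the antipsychotic comes first.
- **That glucose and lipid changes are distorted too.** Nothing in the documents shows that a shift of up to 24 hours matters for them, and the Phase 1 summary reports chemistry other than prolactin as relatively unchanged.
- **That the footnote costs ACTH and cortisol their baseline.** Their schedule row does not carry this footnote. They do lack a Screening draw, so a post-dose Day 1 sample would leave no baseline, but that comes from a separate missing pre-dose rule.

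**Conclusion.** The point stands in a limited form. The footnote permits a post-dose Day 1 sample, and it permits a Day 28 sample drawn on Day 29 after standard antipsychotic treatment has begun. It does so against the schedule header and Section 7.2.10, and neither document removes or marks the second kind of value.

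The direction at Day 1 is clear if the Screening prolactin is still raised by a previous antipsychotic: the reported rise is too small and a normal-to-high shift can be missed. At Day 28 the direction depends on the drug prescribed. The size cannot be given. The documents state neither how many samples would fall in the affected hours nor any patient prolactin level, and the randomized number is blacked out.

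The reach is confined to descriptive safety tables, chiefly prolactin. The conclusion assumes that sites may use the footnote as written. It is a correction worth making because it costs almost nothing, not because it threatens the trial's main result.

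**What to change.** 1. **Footnote.** Keep ±24 hours for Days 8, 15 and 21 only, which matches the schedule header.
2. **Day 1.** State that laboratory samples are drawn before the first dose. Add the same words for ACTH and cortisol, which have no Screening sample to fall back on.
3. **Day 28.** Reconcile the laboratory footnote, the schedule header, Section 7.2.10, the footnote on restarting antipsychotics, and Section 7.2.11. The documents do not settle which should prevail. The change concerns when blood is drawn and not when any treatment starts.
4. **SAP.** Add one line to Section 5.13.2: exclude or flag any laboratory value mapped to Day 28, including early termination values through Day 30 under Table 3, that was drawn after the first standard antipsychotic dose. This needs the clock time of that dose, which the items listed for concomitant medications in Protocol Section 6.7 do not include. If only dates are held, flag samples that share the date of that dose.

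The cost is a few lines of text and one derived flag. Patients are inpatients and already fasting, so no extra draw is needed. The downside is that a few Day 28 values may be flagged or lost. If sampling is already complete, item 4 can still be applied before database lock.

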in total PANSS score between the Screening and Baseline assessments will be excluded from study participation. SCI-PANSS will be administered first on visits before any other scales, when SCI-PANSS and CGI-S are being administered with the exception of Screening where MINI-Plus BPD 7.0.2 will be administered first.

The Placebo-Control Reminder Script[©] Hassman and Cohen, 2019, Version 5.0 educates clinical trial subjects of key causes of the placebo and nocebo effects, level setting of the subject's study expectations, reminding subjects what a placebo is and how that relates to their reporting of symptoms and potential side effects, and explaining how interactions with research site staff differ from their experience with clinical providers. The PCRS informs subjects that they are to be honest about their symptoms and that the site staff have no expectations of symptom improvement or worsening and will not be disappointed by the subject's responses, and asks subjects to explain in their own words PCRS content to ensure comprehension. The PANSS Rater will read the PCRS before administering the PANSS at each study visit.

- During Screening, patients will undergo a practice assessment of the Cogstate test. On Day 1 and Day 28, the actual Cogstate testing will be performed. Note: Cogstate Battery test creot be done within 8 hours of receiving a benzodiazepine or sleep medication.
- To include height at the Screening Visit only. A full physical examination will be conducted at the Screening Visit and at EoT Visit. At each other study visit, patients will be assessed for continued dosing and any possible physical symptoms and a targeted physical examination may be performed, if indicated.
- k. On Days 1, 8, 15, 21, and 28, the SAS, BARS, and AIMS assessments are to be conducted 3 to 6 hours after the administration of study treatment with the exception of ET Visit.
- 1. If the administration of C-SSRS at Screening highlights the risk of suicide not previously known, in the opinion of the Investigator, the patient should be excluded from the trial. At this visit the "Baseline/Screening" version of the C-SSRS scale will be used.
- m. At all other study visits the "Since Last Visit" version of the C-SSRS scale should be used.
- ^{n.} BMI; derived programmatically from body weight and height measurements.

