8.3 Pharmacokinetic Assessments

Details of the procedures to be followed for sample collection, storage, and shipment will be documented in a separate Laboratory Manual.

These samples will not be used to assess biomarkers or genetic markers.

PK plasma samples will be analyzed for concentrations of LB-102 applicable based on randomization. PK analyses will include the randomized in the study regardless of cohort and PK blood samples will be collected on Day 1, 8, and 21 at the following timepoints after the morning dose: 15 minutes, 30 minutes, 1, 2, 3, 4, 8, and 24 hours. On Day 1 only, a pre-dose PK blood sample will be collected.

The following windows for PK collection are allowed:

- Pre-dose PK can be drawn up to 60 minutes prior to first dose.
- \pm 5 minutes window on the 15 minutes, 30 minutes, 1, 2, 3, 4, 8 hours, PK collection times.
- ±15 minutes window on 24-hour PK collection time.

Note: The 24-hour PK must be drawn prior to next applicable dose.

Plasma concentrations of LB-102 will be measured during the study and PK parameters derived using noncompartmental or compartmental methods as appropriate. The following PK parameters (as appropriate) will be calculated: area under the concentration-time curve from time zero to time (AUC_{0-t}), area under the concentration-time curve from time of dosing up to 24 hours (AUC₀₋₂₄), area under the concentration-time curve from time zero to infinity (AUC_{0-inf}), area under the concentration-time curve extrapolated from time t to infinity as a percentage of the total AUC (AUC_{wextrap}), oral clearance (CL/F), maximum concentration (C_{max}), time to reach C_{max} (T_{max}), terminal elimination rate constant (λ_z), and apparent terminal half-life ($t_{1/2}$).

No value for λ_z , AUC_{0-inf}, CL/F, or $t_{1/2}$ will be reported for cases that do not exhibit a terminal log-linear phase in the concentration versus time profile.

No PK parameters will be calculated for patients with detectable concentrations for 2 or fewer time points.

Individual and mean plasma concentration-time curves (both linear and log-linear) will be included in the final report.

PK parameters of LB-102 will be summarized by cohort using descriptive statistics (sample size, arithmetic means, geometric means, standard deviation [SD], % coefficient of variation [CV], minimum, median, and maximum). Figures will be created to

Confidential Page 71 of 102

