## 5.12 Pharmacokinetic Analyses

Blood samples for determination of plasma concentrations of drug will be collected on Day 1, 8 and 21 at the following time-points: pre-dose (only at Day 1), 15 minutes, 30 minutes, 1, 2, 3, 4, 8, and 24 hours post dose. Concentration-time data will be tabulated by nominal (planned) time, analyte, and treatment using descriptive statistics. For presentation of the individual data and summary statistics, concentrations below the limit of quantitation (BLQ) will be set to half the lower limit of quantitation (LLOQ).

Individual patient and mean plasma concentration-time data will be presented graphically on linear and semi-logarithmic scales. Mean data will be plotted using nominal sample times, and individual data will be plotted using actual times.

The following PK parameters will also be summarized by analyte and treatment using descriptive statistics: area under the concentration-time curve from time zero to time (AUC0-t), area under the concentration-time curve from time of dosing up to 24 hours (AUC0-24), area under the concentration-time curve from time zero to infinity (AUC0-inf), area under the concentration-time curve from time 0 to the last available sampling time (AUClast), area under the concentration-time curve extrapolated from time t to infinity as a percentage of the total AUC (AUC%extrap), oral clearance (CL/F), maximum concentration (Cmax), time to reach Cmax (Tmax), terminal elimination rate constant ( $\lambda_z$ ), and apparent terminal half-life (t1/2).

Dose proportionality will be assessed by using a power model separately for the Cmax and AUClast separately for each applicable visit. In this model the log-transformed PK parameter of interest will be considered as the response variable and the log-transformed dose (i.e. 50, 75 and 100 mg) will be the only model covariate. The model will be fit using the following sample SAS code:

```
ods output parameterestimates = parms;
proc mixed data =  plots = none;
  by visit;
  model logaval = logdose / ddfm = kr;
run;
```

From the above model the slope estimate  $\beta$  will be derived alongside its 90% confidence interval, and dose proportionality will be met if the confidence intervals lie entirely within this range:

$$1 + \frac{\ln(\Theta_L)}{\ln(r)} \text{ to } 1 + \frac{\ln(\Theta_H)}{\ln(r)}$$

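### No on-treatment ECG is required near peak drug level, and in the first 60 (PK-sampled) patients the Day 8 and Day 21 ECGs must fall before dosing or within about 20 minutes after it

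*Protocol*

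**What the plan says.** Triplicate ECGs are scheduled on Days 1, 8, 15, 21 and 28 (or early termination). Neither Protocol Section 7.1 nor Section 8.2.3 gives a time from dose. The only timing rule is one of order, and it appears in several places:

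- ECG footnote to Section 7.1, repeated in 8.2.3: "ECGs scheduled for the same visit as blood samples are to be completed before blood is drawn".
- Laboratory footnotes: "Vital signs and ECG should be completed before any blood samples are collected".
- PK footnote: "Samples are collected after ECGs and vital signs".

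The PK footnote also states who is sampled: "PK analyses will include the First 60 randomized patients regardless of cohort". SAP Section 5.12 gives the schedule as "collected on Day 1, 8 and 21 at the following time-points: pre-dose (only at Day 1), 15 minutes, 30 minutes", continuing to 24 hours. Protocol Section 8.3 allows a plus-or-minus "5 minutes window on the 15 minutes, 30 minutes, 1, 2, 3, 4, 8 hours, PK collection times". Sections 7.2.4 and 7.2.8 require each visit's assessments to be done on one day.

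The extrapyramidal scales at the same visits are tied to dose: "the SAS, BARS, and AIMS assessments are to be conducted 3 to 6 hours after the administration of study treatment".

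SAP Section 5.13.4 summarizes QTcF and its change from Baseline by visit, with no reference to the interval between dose and ECG.

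**The concern.** QTcF prolongation is a named risk in Protocol Section 1.8.1 and has its own individual stopping rule in Section 4.1.1.2 (above 500 msec, or more than 60 msec over Baseline). In Phase 1 (Section 14.2), QTcF rose 20-46 msec from pre-dose values in all volunteers on 200 mg, and the next cohort was reduced to 150 mg for that reason. If any QTcF effect follows plasma concentration, ECGs taken before dosing or during early absorption will show less of it than ECGs near peak.

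The schedule forces early readings in one group of patients and leaves timing open in the rest. The Day 8 and Day 21 summaries therefore mix readings forced to low exposure with untimed ones, and the Day 15 and Day 28 summaries are wholly untimed. At stake is how well the trial describes QTcF at 50, 75 and 100 mg, as part of its secondary safety objective. The primary efficacy analysis is not affected.

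**Working it through.** The plan states no figure for ECG exposure, so there is none to reproduce.

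**1. Latest possible ECG on a PK day.** On Days 8 and 21 the first blood sample for PK is at 15 minutes, at the latest 15 + 5 = 20 minutes after dosing. The ECG comes first and on the same day, so it is pre-dose or at most about 20 minutes post-dose. The post-dose option is feasible: 5 minutes supine plus two 1-minute gaps is 7 minutes, and vital signs in three positions add 3 × 3 = 9 minutes, making 16.

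**2. Distance from peak.** Protocol Table 14.1 gives median Tmax of 3 h (range 2-4) at 50 mg and 3.01 h (range 1-4) at 100 mg. A 20-minute ECG is about 2 h 40 min before the median peak.

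**3. The other on-treatment ECGs.** These are Days 15 and 28 in everyone, and Days 8 and 21 outside the first 60. They need only precede a fasting laboratory draw, which has no stated time from dose and is a loose anchor: "Clinical laboratory test results drawn within ± 24 hours of the scheduled timepoint may be used". A near-peak reading is allowed but never required.

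**4. Pre-dose exposure as a share of steady-state peak.** Means from Table 14.1, with once-daily superposition assumed:

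| Step | 50 mg | 100 mg |
|---|---|---|
| Cmax (ng/mL) | 176 | 348.2 |
| λz (/h) | 0.0592 | 0.0521 |
| AUC0-inf − AUC0-24 | 1595.9 − 1336.1 = 259.8 | 2809.8 − 2303.7 = 506.1 |
| C24 = AUC tail × λz | 15.4 | 26.4 |
| R = 1/(1 − exp(−24λz)) | 1.318 | 1.401 |
| Trough = C24 × R | 20.3 | 37.0 |
| Peak = Cmax + trough × exp(−λz × Tmax) | 193.0 | 379.8 |
| Trough / peak | 10.5% | 9.7% |

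This is rough. At 100 mg the AUC difference (506) is about the size of the SDs of the two AUCs (478 and 533). As an upper bound, suppose the whole fall from peak ran at the terminal rate: exp(−λz × (24 − Tmax)) = 28.8% and 33.5%. The decline is described as biphasic, so the true ratio should be lower.

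**5. Exposure at 20 minutes (illustration only).** Assume first-order absorption, with ka solved from ln(ka/λz)/(ka − λz) = Tmax. This gives 1.002 and 1.050 /h. With g(t) = exp(−λz t) − exp(−ka t), C(20 min) = trough × exp(−λz/3) + Cmax × g(1/3)/g(Tmax) = 79.0 and 155.5 ng/mL, about 41% of peak at both doses.

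The absorption shape is not reliable enough for more than illustration. Taken as a full one-compartment curve, it implies AUC0-inf = [Cmax/g(Tmax)] × (1/λz − 1/ka) = about 3,551 and 7,817, against the tabulated 1,596 and 2,810. It is too large by factors of 2.2 and 2.8, so no one-compartment percentages are used here.

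**6. Number of ECGs forced early.** At 3:3:3:1 the first 60 split as 18, 18, 18 and 6, with 18 + 18 + 6 = 42 on LB-102. Two forced visits each gives 42 × 2 = 84, before drop-out.

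**The case against.** The strongest reply is about weight. The 84 ECGs are half of the 42 × 4 = 168 scheduled in PK-sampled LB-102 patients, but SAP Section 5.13.4 pools all patients. A reader might infer that half of the on-treatment ECG data are compromised. The documents do not support that: total N is redacted, so the overall share is unknown, and Days 15 and 28 contain no forced readings. This stands.

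A reader might also infer that patients meeting the QTcF stopping rule will be missed. The documents do not show this either. They give no concentration-QTc relation, the 20-46 msec rise was at twice the top dose here, and predefined Phase 1 stopping criteria were not met. The trial also has entry exclusions on QTcF and conduction, prohibited CYP inhibitors, site and central ECG reading, a Safety Review Committee and unscheduled visits for adverse events. This stands too, and it limits the point to the quality of the QTcF description.

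Third, the before-blood order is deliberate, and moving the ECG has a price: the individual comparison with Baseline then spans different times of day. That is a real cost but a small one.

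Finally, a laboratory manual or safety plan outside these documents might set ECG times. That is possible. However, any time later than about 20 minutes on a PK day would conflict with the protocol as written.

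**Conclusion.** The timing point holds as a deduction from the protocol's own rules. In the first 60 patients the Day 8 and Day 21 ECGs fall before dosing or within about 20 minutes after, against a median Tmax of about 3 h, and no other scheduled on-treatment ECG has to be near peak. The by-visit QTcF summaries can therefore understate the peak effect.

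Pre-dose exposure is roughly 10% of steady-state peak, and at most 29-34%. This rests on single-dose healthy-volunteer means with six per dose, on superposition, and on 50 and 100 mg bracketing 75 mg, which Table 14.1 does not include. Exposure at 20 minutes is less certain. At 100 mg the earliest individual Tmax was 1 h, so not every patient would be far below peak by then. About 84 ECGs in about 42 LB-102 patients are affected, if the first 60 follow the allocation ratio and reach Day 21.

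Day 1 is a drug-free Baseline and is not part of the point. No size in msec can be computed. This is a worthwhile, cheap improvement to safety measurement, not a demonstrated safety failure.

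**What to change.** In Protocol Sections 7.1 (laboratory, ECG and PK footnotes), 7.2.4, 7.2.6, 7.2.8, 7.2.10 and 8.2.3:

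- Time the existing triplicate ECG on Days 8, 15, 21 and 28 to about 2-4 h post-dose, except at an early termination visit.
- On PK days, complete it just before the 3 h sample and the extrapyramidal scales.
- Exempt it from the before-blood rule for the fasting laboratory draw and the earlier PK draws.
- Keep the supine rest of at least 5 minutes and the pre-dose Day 1 Baseline.

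Optionally, in SAP Section 5.13.4, report the dose-to-ECG interval and tabulate by arm the patients with QTcF above 500 msec or more than 60 msec over Baseline.

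The change adds no ECGs. Patients are inpatients, and staff already assess them at 3-6 h. There are two costs. On PK days the ECG follows several blood draws and must fit around samples with 5-minute windows. Baseline and on-treatment ECGs also fall at different times of day. The placebo arm controls that for group comparisons but not for the individual rule of more than 60 msec over Baseline, where the confirmatory reading within 15 minutes is only a partial safeguard.
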